7.3 Assessment of Causality and Expectedness

A medically-qualified investigator must assess the relationship of any AE to the use of study drug, based on available information, using the following guidelines:

Causality

Possibly Related - There is a reasonable possibility that the adverse event may have been caused by the study drug. The temporal relationship of the adverse event to study drug administration makes a causal relationship possible, and other drugs, therapeutic interventions or underlying conditions do not provide sufficient explanation for the observed event.

Not Possibly Related- It is unlikely that the event was caused by the study drug. The temporal relationship of the adverse event to the study drug administration makes causal relationship unlikely and other drugs, therapeutic interventions or underlying conditions provide a more likely explanation for the event.

Expectedness

The expectedness of an adverse event or suspected adverse reaction shall be determined according to the package insert for U.S. marketed furosemide and dapagliflozin. Any AE that is not identified in nature, severity, or specificity in the current U.S. package insert is considered unexpected. Events described in the U.S. package insert as occurring with a class of drugs or as anticipated from the pharmacological properties of the drug, but not specifically mentioned as occurring with the particular drug under investigation are considered unexpected.

7.4 Reporting of Adverse Events and SAEs

All adverse events occurring from signing of the Informed Consent through the 30-day follow-up period will be collected and reported. The Site Investigator is responsible for monitoring the safety of patients enrolled into the study. The following adverse events are anticipated, disease related-events in patients with decompensated heart failure; however, they should still be reported on the Adverse Event form in the REDCAP Database (some may require reporting as study endpoints):

- New Ventricular Arrhythmia: Ventricular tachycardia lasting longer than 30 seconds, or frequent non-sustained VT causing hemodynamic instability with MAP < 60 mmHg requiring intervention or > 1 intra-cardiac defibrillation or external cardiac defibrillation shock or ventricular fibrillation requiring defibrillation or requiring transfer to the intensive care unit
- Hypotension: SBP < 90 for 2 repeated measurements within 30 minutes or lasting at least 30 minutes or symptomatic hypotension necessitating clinical intervention (defined as vasopressor support, intravenous fluid boluses, or initiation of inotropes)
 - Hypovolemic hypotension: subset of "hypotension" requiring fluid administration for hypovolemia
- *Cardiac arrest*: any ventricular arrhythmic or pulseless electrical event that requires immediate life-sustaining medical therapies
- Acute kidney injury requiring renal replacement therapy: an acute renal failure event that began during the study period and necessitates new renal replacement therapy during the hospitalization
- Prolonged hospitalization as a result of the following safety outcomes: hypotension requiring medical intervention or hypoglycemia requiring medical intervention
- Diabetic ketoacidosis as adjudicated by the CEC
- Death

All serious adverse events must be recorded in the Adverse Event Record of the patient's REDCAP database. All serious adverse events should be monitored until stabilization or resolution.

The process of reporting of SAEs will be as follows:

- 1. The investigator team informs the site investigator of an SAE
- 2. The site investigator reports the SAE to the local IRB and to the coordinating center and PI within 24 hours of being aware of the event. The site investigator will electronically submit the necessary supporting documentation to the coordinating site.
- 3. The coordinating center and PI will report the SAE to AstraZeneca.
- 4. If the coordinating set determines the SAE is a SUSAR, the coordinating site will report the SUSAR to the FDA.

Reporting to the Coordinating Site

All serious adverse events will be reported to the coordinating center (Vanderbilt) by the investigational site within 24 business hours of being aware of the event.

Reporting to Local IRB. Investigators are also responsible for promptly reporting unexpected adverse events (serious and non-serious) to their reviewing IRB in accordance with local requirements. The Vanderbilt investigational site will report DSMB reports to the Vanderbilt IRB annually at the time of continuing review at a minimum. SAEs will be reported to the local IRB within 24 business hours of being aware of the event.

Reporting to the Data Safety Monitoring Board

Adverse event reports will be generated and presented to the DSMB at each meeting for review. The DSMB will also be alerted to SAEs prior to scheduled meetings if the number of individual SAEs in the data safety and monitoring plan are met.

Reporting to AstraZeneca

The coordinating center will notify AstraZeneca of each SAE. The SAE will be submitted as an individual case report. The causality of SAEs (their relationship to all study treatments/procedures) will be assessed by the investigator(s) and communicated to AstraZeneca. The Investigator is responsible for informing the local authorities (FDA) and ethical committees, of any SAEs as per local requirements, and concurrently AstraZeneca. When reporting to AstraZeneca, a cover page will accompany the SAE form indicating the following:

- External Sponsored Research (ESR)
- The site investigator's and coordinating center's name and address
- The trial name/title and AstraZeneca ESR reference number

SAEs will be reported by way of fax to AstraZeneca's designated fax line: [contact] or email if a secure is set up: [contact]

7.5 Study Termination

The study may be terminated based on the DSMB review of serious adverse events and unexpected events.

7.6 Non-serious Adverse Events

Non-serious AEs will be reported to the IRB and AstraZeneca in annual scheduled reports. Additionally, the investigator will notify AstraZeneca of all non-serious AEs as a line item list at the end of the study. Non-serious AEs will be presented to the DSMB at each interim analysis.

The following events are examples of potential non-serious suspected adverse reactions unless the seriousness meets criteria for a SAE as defined above.

- Incidence of mycotic genital infection, defined as a new symptomatic infection requiring treatment
- Incidence of symptomatic cystitis, defined as new symptoms of dysuria, frequency, and/or urgency, plus a urine culture with at least 10² colony forming units of a uropathogen requiring treatment with antibiotic therapy
- Incidence of symptomatic pyelonephritis, defined as new symptoms of dysuria, frequency, and/or urgency plus acute flank pain, plus a urine culture with at least 10² colony forming units of a uropathogen requiring treatment with antibiotic therapy

7.7 Pregnancy

Pregnancy is an exclusion criteria for this trial. It is unlikely that a patient would become pregnant during this study, as it takes place during hospitalization for acute heart failure. If a patient becomes pregnant during the course of the study, dapagliflozin will be discontinued immediately and an Astra Zeneca representative notified. Pregnancy itself is not regarded as an AE unless there is a suspicion that dapagliflozin may have interfered with the effectiveness of a contraceptive medication. The outcome of all pregnancies (spontaneous miscarriage, elective termination, ectopic pregnancy, normal birth or congenital abnormality) will be followed up and documented even if the patient was discontinued from the study. All pregnancies and outcomes of pregnancy will be reported to AstraZeneca's designated fax line: [contact] or email: [contact]

8.0 Data Handling and Record Keeping

The primary data collection system for our study will be the REDCap system, which uses a web-based electronic data capture. All data collected at any point in the trial are entered into this EDC system. At regular intervals, all data will be transferred from the EDC database for statistical summarization, data description, and data analysis. Further crosschecking of the data will be performed, and discrepant observations flagged and appropriately resolved through a data query system. The biostatistical team will perform internal database quality-control checks, and data audits throughout the course of the trial.

8.1 Data Confidentiality and Retention

Computerized data will be accessible only by password, and a centralized monitoring system will record and report all access to data. Electronic CRFs (eCRFs) will be identified by study number only, to ensure participant anonymity. No participant identifiers will be used in the presentation of data. Study records that might identify participants will be kept confidential as required by law. Except when required by law, participants will not be identified by name, personal identification number (e.g. social security number, social insurance number), address, telephone number, or any other direct personal identifier in study records. Participants will be informed that the study physician and his/her study team will report the results of study-related tests to the investigators and to the NIH. Participants will be informed that their records may be reviewed in order to meet federal, state or regional/local regulations. Reviewers may include the study team monitors, IRBs/ECs, the NIH, other government regulators as dictated by local law, or their delegates. Study records will be maintained by the investigators for a period of six (6) years following the expiration of the grant or length of time as required by local regulations, whichever is longer.

9.0 Study Withdrawal/Discontinuation

A patient may withdraw at the study at any time. The patient will inform the site investigator of their desire to withdraw. All study-based therapy will stop at this point, and the attending cardiologist will perform any further care. All study data collected to that time point will be included in the analysis. The withdrawal reason will be documented. All patients will be followed per the study protocol through Day 30.

10.0 Statistical Methods

The full statistical methods are detailed separately in the Statistical Analysis Plan.

The primary analysis model will be the semiparametric proportional odds (PO) ordinal logistic regression model¹⁶ for continuous outcome variables¹⁷. The PO model does not make any distributional assumption for the response variable, is robust to extreme values, and is invariant to transformations of the response variable. It is also extremely efficient when compared to linear regression if normality holds. The Wilcoxon nonparametric two-sample test is a special case of the PO model, but the PO model allows for baseline covariate adjustment. Note that we use covariate adjustment instead of change from baseline so as to not assume that (1) the baseline variable is linearly related to the response variable and (2) the slope of the baseline variable is 1.0.

For binary outcomes we will use the special case of the PO model that is the binary logistic regression model.

For safety analysis of clinical lab variables we use the most powerful and least arbitrary continuous variable analyses and include the empirical cumulative distribution function of post-randomization values of these variables. These continuous analyses will also provide estimates of incidence of such outcomes as hyper- and hypo-kalemia, but will be more sensitive than using only binary responses.

Trial	Experimental agent	Mean decrease in weight (kg) Experimental, (%)	Mean decrease in weight Control, (%)	Within group SD in Experimental Group (kg)
TRUE-AHF ⁸	Ularitide			
RELAX-AHF ¹⁸	Serelaxin	3.6	3.0	4.4
ASCEND-HF ⁹	Nesirtide			
EVEREST ¹⁹	Tolvaptan	3.3	2.7	3.3
TACTICS ²⁰	Tolvaptan	3.7	2.5	4.4
Secrets of HF ²¹	Tolvaptan	3.5	2.4	2.0
ROSE-HF ²²	Nesiritide	3.25	3.5	0.9
ROSE-HF ²²	Dopamine	3.4	3.5	0.9
MEAN		3.5	2.9	2.7

Changes in body weight from admission to discharge in previous literature

Changes in weight by IV 40mg Furosemide Equivalents (FE)

Trial	Experimental agent	Duration (days)	Daily IV loop diuretic dose in FE, mean or median (IQR)*	Median (IQR) decrease in weight (kg)/40mg IV FE	Difference associated with adverse HF outcomes
RELAX-AHF ²³	Serelaxin	5	80	0.42 (1.00, 0.14)	Below median value
DIUR-HF ¹⁴	None	3-5	137 (100, 200)	0.20 (0.281, 0.082)	Below median value
ASCEND-HF ²⁴	Nesiritide	2		0.42 (1.0, 0.05)	Below median value
PROTECT ²⁵	Rolofylline	4	80 (47, 133)	0.38 (0.8, 0.13)	Below median value
EVEREST ^{19,26}	Tolvaptan	4	80	0.30 (0.79, 0.03)	Below median value
Average across clinical trials				0.34 (0.78, 0.09)	

FE= Furosemide Equivalents (FE)

Multiple clinical trials have examined and validated the diuretic efficiency metric of mean weight loss (kg)/40mg IV furosemide in contemporary AHF study populations. ^{14 14 14 14} The average cumulative median weight loss/40mg furosemide across these trials was 0.34 (IQR 0.78, 0.09) kg/40mg. Patients with this diuretic efficiency metric in the lower two quartiles had higher incidence of adverse outcomes including hospitalization and mortality across time frames of 30 to 180 days after multivariate analyses. These findings have been confirmed by diuretic efficiency metrics using urine output/40mg IV furosemide in several other populations. In an AHF population at our medical center, we also found a the weight based diuretic efficiency to be similar, with a mean 0.25 kg/40mg but a higher standard deviation (0.47 kg/40mg).

We anticipate dapagliflozin to increase the weight loss while decreasing the cumulative furosemide dose required to achieve euvolemia. On the basis of the historical literature, we project an increase in diuretic efficiency by 0.1kg/40mg IV furosemide in the dapagliflozin arm to be a clinically meaningful difference. We project that our diuretic protocol will decrease variations in loop diuretic dosing, which drive large standard deviations. We project a normally distributed standard deviation within each arm to be 0.25kg/40mg. A sample size of 120 experimental subjects and 120 control subjects will have 87% power to detect a probability of 0.611 that an observation in the dapagliflozin arm is less than an observation in the standard of care arm using a Wilcoxon (Mann-Whitney) rank-sum test with a 0.05 two-sided significance level.

For descriptive statistical analyses of baseline characteristics we will compute proportions for categorical data. Continuous variables will be described by sample quantiles, mean, and Gini's mean differencewill be described using sample quantiles.

References:

- 1. Adams KF, Jr., Fonarow GC, Emerman CL, et al. Characteristics and outcomes of patients hospitalized for heart failure in the United States: rationale, design, and preliminary observations from the first 100,000 cases in the Acute Decompensated Heart Failure National Registry (ADHERE). *American heart journal.* 2005;149(2):209-216.

Appendix A: Schedule of study assessments

HgbA1c= hemoglobin A1c; BNP= b-type natriuretic peptide; CV = cardiovascular

* Urine sodium, urine potassium, and urine creatinine collected approximately 2 hours after an IV loop diuretic dose. For baseline, this can be 2 hours after the first open-label IV loop diuretic dose prior to randomization. **Vital Signs and weights are done as close to randomization time as possible for each day

***24 h urine collection started on day 2 plus or minus 6 hours from randomization

[†] At Vanderbilt University Medical Center study site only

Appendix B: Insulin algorithms for patients with Type 2 diabetes

Insulin lispro is listed as the rapid acting insulin but may be substituted with a equivalent rapid acting insulin for formulary differences across investigation sites

Insulin glargine is listed as the long acting insulin but may be substituted with a equivalent long acting insulin for formulary differences across investigation sites

*Correctional Insulin regimens based upon blood glucose measured 4 times daily (before meals and at bedtime or every 6 hours if NPO):

Blood Glucose	Moderate dose correctional scale
< 70 mg/dl	Hypoglycemia protocol per hospital protocol
70 -139mg/dl	No action
140 - 159mg/dl	1 unit insulin lispro
160 - 189 mg/dl	2 units insulin lispro
190- 219 mg/dl	3 units insulin lispro
220 - 249 mg/dl	4 units insulin lispro
250 - 279mg/dl	5 units insulin lispro
280 - 309mg/dl	6 units insulin lispro
310 - 339mg/dl	7 units insulin lispro
340 - 369mg/dl	8 units insulin lispro
370 - 379mg/dl	9 units insulin lispro
>380mg/dl	10 units insulin lispro and notify medical team

Blood Glucose	High dose correctional scale
< 70 mg/dl	Hypoglycemia protocol per hospital protocol
70 -139mg/dl	No action
140 - 159mg/dl	2 units insulin lispro
160 - 179 mg/dl	3 units insulin lispro
180 - 199 mg/dl	4 units insulin lispro
200 - 219 mg/dl	5 units insulin lispro
220 - 239mg/dl	6 units insulin lispro
240 - 259mg/dl	7 units insulin lispro

260 - 279mg/dl	8 units insulin lispro
280 - 299mg/dl	9 units insulin lispro
300 - 319mg/dl	10 units insulin lispro
300 - 319mg/dl	10 units insulin lispro
320 - 339mg/dl	11 units insulin lispro
340 - 359mg/dl	12 units insulin lispro
360 - 379mg/dl	13 units insulin lispro
380 - 399mg/dl	14 units insulin lispro
>400mg/dl	15 units insulin lispro and notify medical team
Blood Glucose Very high dose correctional scale	
	, 5
< 70 mg/dl	Hypoglycemia protocol per hospital protocol
70 -139mg/dl	No action
140 - 174mg/dl	3 units insulin lispro
175 - 204 mg/dl	5 units insulin lispro
205 - 234 mg/dl	7 units insulin lispro
235 - 264mg/dl	9 units insulin lispro
265 - 294mg/dl	11 units insulin lispro
295 - 324mg/dl	13 units insulin lispro
325 - 354mg/dl	15 units insulin lispro
355 - 384mg/dl	17 units insulin lispro
385 - 399mg/dl	19 units insulin lispro
>400mg/dl	20 units insulin lispro and notify medical team

[#]Basal insulin regimen

Glarg	ine once daily - starting daily dose:
•	Patients with BG between 140-200 mg/dL= 0.2 units per kg weight per day.
٠	Patients with BG between 201-400 mg/dL= 0.25 units per kg weight per day.
٠	Glargine insulin will be given once daily, at the same time of the day.
•	Patients will receive the full-dose of glargine insulin (even if NPO) except for those that have GFR <50 ml/min.
•	Patients with GFR <50ml/min will receive only one-half of the calculated insulin dose
Supp	lemental (correction) insulin:
•	Give supplemental insulin lispro following the "correctional scale" protocol* for elevated blood glucose
٠	If a patient is able and expected to eat all, give supplemental lispro insulin after each meal and at bedtime following the high dose correctional scale
٠	If a patient is not able to eat, give supplemental lispro insulin every 6 hours (6-12-6-12) following the moderate dose correctional scale
Daily	insulin adjustment:
	Easting and pro-moal BC between 100, 140 mg/dl without hypoglycomia the

 Fasting and pre-meal BG between 100-140 mg/dl without hypoglycemia the previous day: no change

- Fasting and pre-meal BG between 141-180 mg/dl: increase glargine dose by 10% every day
- Fasting and pre-meal BG >180 mg/dl: increase glargine dose by 20% every day
- Fasting and pre-meal BG between 70-99 mg/dl: decrease glargine dose by 10% every day
- If a patient develops hypoglycemia (BG <70 mg/dL), decrease glargine dose by 20%.
- If a patient develops hypoglycemia (BG <40 mg/dL), decrease glargine dose by 30-40%.

Blood glucose monitoring:

• Measure BG before each meal and at bedtime (or every 6 hours if a patient is not eating) using a glucometer.

^{\$}Basal and Bolus Meal Coverage Insulin

 Glargine once daily - starting daily dose: Patients with BG between 140-200 mg/dL= 0.4 units per kg weight per day. Patients with BG between 201-400 mg/dL= 0.5 units per kg weight per day. Half the total insulin daily dose will be given as glargine and the other half as lispro. Glargine insulin will be given once daily, at the same time of the day. Patients will receive the full-dose of glargine insulin (even if NPO) except for those that have GFR <50 ml/min. Patients with GFR <50 ml/min. Patients with GFR <50 ml/min will receive only one-half of the calculated insulin dose Insulin lispro will be given in three equally divided doses after each meal. To prevent hypoglycemia, if a subject is not able to eat, the dose of lispro will be held. Patients with GFR <50ml/min receive one-half of the calculated insulin dose. Supplemental (correction) insulin: Give supplemental insulin lispro following the "correctional scale" protocol* for elevated blood glucose If a patient is able and expected to eat all, give supplemental lispro insulin after each meal and at bedtime following the high dose correctional scale If a patient is not able to eat, give supplemental lispro insulin every 6 hours (6-12-6-12) following the moderate dose correctional scale Fasting and pre-meal BG between 100-140 mg/dl without hypoglycemia the previous day: no change 		
 Patients with BG between 201-400 mg/dL= 0.5 units per kg weight per day. Half the total insulin daily dose will be given as glargine and the other half as lispro. Glargine insulin will be given once daily, at the same time of the day. Patients will receive the full-dose of glargine insulin (even if NPO) except for those that have GFR <50 ml/min. Patients with GFR <50ml/min will receive only one-half of the calculated insulin dose Insulin lispro will be given in three equally divided doses after each meal. To prevent hypoglycemia, if a subject is not able to eat, the dose of lispro will be held. Patients with GFR <50ml/min receive one-half of the calculated insulin dose. Supplemental (correction) insulin: Give supplemental insulin lispro following the "correctional scale" protocol* for elevated blood glucose If a patient is able and expected to eat all, give supplemental lispro insulin after each meal and at bedtime following the high dose correctional scale If a patient is not able to eat, give supplemental lispro insulin every 6 hours (6-12-6-12) following the moderate dose correctional scale Fasting and pre-meal BG between 100-140 mg/dl without hypoglycemia the previous day: no change 	Glargi	ne once daily - starting daily dose:
 Half the total insulin daily dose will be given as glargine and the other half as lispro. Glargine insulin will be given once daily, at the same time of the day. Patients will receive the full-dose of glargine insulin (even if NPO) except for those that have GFR <50 ml/min. Patients with GFR <50ml/min will receive only one-half of the calculated insulin dose Insulin lispro will be given in three equally divided doses after each meal. To prevent hypoglycemia, if a subject is not able to eat, the dose of lispro will be held. Patients with GFR <50ml/min receive one-half of the calculated insulin dose. Supplemental (correction) insulin: Give supplemental insulin lispro following the "correctional scale" protocol* for elevated blood glucose If a patient is able and expected to eat all, give supplemental lispro insulin after each meal and at bedtime following the high dose correctional scale If a patient is not able to eat, give supplemental lispro insulin after each meal and at bedtime following the high dose correctional scale If a patient is not able to eat, give supplemental lispro insulin every 6 hours (6-12-6-12) following the moderate dose correctional scale Fasting and pre-meal BG between 100-140 mg/dl without hypoglycemia the previous day: no change 	•	Patients with BG between 140-200 mg/dL= 0.4 units per kg weight per day.
 lispro. Glargine insulin will be given once daily, at the same time of the day. Patients will receive the full-dose of glargine insulin (even if NPO) except for those that have GFR <50 ml/min. Patients with GFR <50ml/min will receive only one-half of the calculated insulin dose Insulin lispro will be given in three equally divided doses after each meal. To prevent hypoglycemia, if a subject is not able to eat, the dose of lispro will be held. Patients with GFR <50ml/min receive one-half of the calculated insulin dose. Supplemental (correction) insulin: Give supplemental insulin lispro following the "correctional scale" protocol* for elevated blood glucose If a patient is able and expected to eat all, give supplemental lispro insulin after each meal and at bedtime following the high dose correctional scale If a patient is not able to eat, give supplemental lispro insulin every 6 hours (6-12-6-12) following the moderate dose correctional scale Fasting and pre-meal BG between 100-140 mg/dl without hypoglycemia the previous day: no change 	•	Patients with BG between 201-400 mg/dL= 0.5 units per kg weight per day.
 Glargine insulin will be given once daily, at the same time of the day. Patients will receive the full-dose of glargine insulin (even if NPO) except for those that have GFR <50 ml/min. Patients with GFR <50ml/min will receive only one-half of the calculated insulin dose Insulin lispro will be given in three equally divided doses after each meal. To prevent hypoglycemia, if a subject is not able to eat, the dose of lispro will be held. Patients with GFR <50ml/min receive one-half of the calculated insulin dose. Supplemental (correction) insulin: Give supplemental insulin lispro following the "correctional scale" protocol* for elevated blood glucose If a patient is able and expected to eat all, give supplemental lispro insulin after each meal and at bedtime following the high dose correctional scale If a patient is not able to eat, give supplemental lispro insulin every 6 hours (6-12-6-12) following the moderate dose correctional scale Fasting and pre-meal BG between 100-140 mg/dl without hypoglycemia the previous day: no change 		
 Patients will receive the full-dose of glargine insulin (even if NPO) except for those that have GFR <50 ml/min. Patients with GFR <50ml/min will receive only one-half of the calculated insulin dose Insulin lispro will be given in three equally divided doses after each meal. To prevent hypoglycemia, if a subject is not able to eat, the dose of lispro will be held. Patients with GFR <50ml/min receive one-half of the calculated insulin dose. Supplemental (correction) insulin: Give supplemental insulin lispro following the "correctional scale" protocol* for elevated blood glucose If a patient is able and expected to eat all, give supplemental lispro insulin after each meal and at bedtime following the high dose correctional scale If a patient is not able to eat, give supplemental lispro insulin every 6 hours (6-12-6-12) following the moderate dose correctional scale Fasting and pre-meal BG between 100-140 mg/dl without hypoglycemia the previous day: no change 		
 those that have GFR <50 ml/min. Patients with GFR <50ml/min will receive only one-half of the calculated insulin dose Insulin lispro will be given in three equally divided doses after each meal. To prevent hypoglycemia, if a subject is not able to eat, the dose of lispro will be held. Patients with GFR <50ml/min receive one-half of the calculated insulin dose. Supplemental (correction) insulin: Give supplemental insulin lispro following the "correctional scale" protocol* for elevated blood glucose If a patient is able and expected to eat all, give supplemental lispro insulin after each meal and at bedtime following the high dose correctional scale If a patient is not able to eat, give supplemental lispro insulin every 6 hours (6-12-6-12) following the moderate dose correctional scale Daily insulin adjustment: Fasting and pre-meal BG between 100-140 mg/dl without hypoglycemia the previous day: no change 	•	Glargine insulin will be given once daily, at the same time of the day.
 dose Insulin lispro will be given in three equally divided doses after each meal. To prevent hypoglycemia, if a subject is not able to eat, the dose of lispro will be held. Patients with GFR <50ml/min receive one-half of the calculated insulin dose. Supplemental (correction) insulin: Give supplemental insulin lispro following the "correctional scale" protocol* for elevated blood glucose If a patient is able and expected to eat all, give supplemental lispro insulin after each meal and at bedtime following the high dose correctional scale If a patient is not able to eat, give supplemental lispro insulin every 6 hours (6-12-6-12) following the moderate dose correctional scale Daily insulin adjustment: Fasting and pre-meal BG between 100-140 mg/dl without hypoglycemia the previous day: no change 		
 prevent hypoglycemia, if a subject is not able to eat, the dose of lispro will be held. Patients with GFR <50ml/min receive one-half of the calculated insulin dose. Supplemental (correction) insulin: Give supplemental insulin lispro following the "correctional scale" protocol* for elevated blood glucose If a patient is able and expected to eat all, give supplemental lispro insulin after each meal and at bedtime following the high dose correctional scale If a patient is not able to eat, give supplemental lispro insulin every 6 hours (6-12-6-12) following the moderate dose correctional scale Daily insulin adjustment: Fasting and pre-meal BG between 100-140 mg/dl without hypoglycemia the previous day: no change 		
 Give supplemental insulin lispro following the "correctional scale" protocol* for elevated blood glucose If a patient is able and expected to eat all, give supplemental lispro insulin after each meal and at bedtime following the high dose correctional scale If a patient is not able to eat, give supplemental lispro insulin every 6 hours (6-12-6-12) following the moderate dose correctional scale Daily insulin adjustment: Fasting and pre-meal BG between 100-140 mg/dl without hypoglycemia the previous day: no change 		prevent hypoglycemia, if a subject is not able to eat, the dose of lispro will be held. Patients with GFR <50ml/min receive one-half of the calculated insulin
 elevated blood glucose If a patient is able and expected to eat all, give supplemental lispro insulin after each meal and at bedtime following the high dose correctional scale If a patient is not able to eat, give supplemental lispro insulin every 6 hours (6-12-6-12) following the moderate dose correctional scale Daily insulin adjustment: Fasting and pre-meal BG between 100-140 mg/dl without hypoglycemia the previous day: no change 	Supple	emental (correction) insulin:
 each meal and at bedtime following the high dose correctional scale If a patient is not able to eat, give supplemental lispro insulin every 6 hours (6-12-6-12) following the moderate dose correctional scale Daily insulin adjustment: Fasting and pre-meal BG between 100-140 mg/dl without hypoglycemia the previous day: no change 	•	
 12-6-12) following the moderate dose correctional scale Daily insulin adjustment: Fasting and pre-meal BG between 100-140 mg/dl without hypoglycemia the previous day: no change 	•	
 Fasting and pre-meal BG between 100-140 mg/dl without hypoglycemia the previous day: no change 	•	
previous day: no change	Daily i	insulin adjustment:
	•	
10% every day	•	Fasting and pre-meal BG between 141-180 mg/dl: increase glargine dose by
 Fasting and pre-meal BG >180 mg/dl: increase glargine dose by 20% every day 		

- Fasting and pre-meal BG between 70-99 mg/dl: decrease glargine dose by 10% every day
- If a patient develops hypoglycemia (BG <70 mg/dL), decrease glargine dose by 20%.
- If a patient develops hypoglycemia (BG <40 mg/dL), decrease glargine dose by 30-40%.

Blood glucose monitoring:

• Measure BG before each meal and at bedtime (or every 6 hours if a patient is not eating) using a glucometer.

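### The basal-bolus insulin table in Appendix B labels total daily insulin as the glargine dose; followed on its heading alone, it doubles starting glargine.

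*Protocol*

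**What the plan says.** Protocol section 5.1 refers sites to Appendix B for starting and titrating insulin. For the basal-bolus regimen, the appendix opens with "Glargine once daily - starting daily dose: Patients with BG between 140-200 mg/dL= 0.4 units per kg weight per day", followed by "Patients with BG between 201-400 mg/dL= 0.5 units per kg weight per day". The next instruction is "Half the total insulin daily dose will be given as glargine and the other half as lispro", with the lispro portion divided equally over three meals. On reduced intake, "Patients will receive the full-dose of glargine insulin (even if NPO) except for those that have GFR <50 ml/min", whereas for lispro, "if a subject is not able to eat, the dose of lispro will be held". Below a GFR of 50 ml/min the calculated dose is halved.

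The basal-only regimen earlier in Appendix B carries the same glargine heading over lower figures: "Patients with BG between 140-200 mg/dL= 0.2 units per kg weight per day" and "Patients with BG between 201-400 mg/dL= 0.25 units per kg weight per day". Both regimens share the same daily adjustment rules, including "Fasting and pre-meal BG between 70-99 mg/dl: decrease glargine dose by 10% every day" and larger cuts after hypoglycemia.

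**The concern.** One figure is labelled as the glargine dose and then treated as a total to be split between two insulins. Both cannot be right. The heading suits the basal-only table, where glargine is the only scheduled insulin, but not the basal-bolus table.

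This is a dosing instruction, not background text. Section 6.0 cites the standardized diabetic protocol as a means of limiting hypoglycemia. Hypoglycemia is a safety outcome in Protocol section 2.4 and is graded by severity in the SAP's safety endpoints, and total daily insulin is an exploratory endpoint in both documents. A site that acted on the heading would give too much long-acting insulin to inpatients whose intake may be poor.

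**Working it through.** No power or sample-size figure is involved; the check is arithmetic on the appendix's own doses.

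**Inputs (Protocol Appendix B)**

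| Glucose band (mg/dL) | Basal-bolus figure (units/kg/day) | Basal-only glargine (units/kg/day) |
|---|---|---|
| 140-200 | 0.4 | 0.2 |
| 201-400 | 0.5 | 0.25 |

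The split is half glargine, half lispro. Body weight is not given in the documents, so 100 kg is assumed, with a range of 70-120 kg.

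**Step 1: which reading is consistent?** Treat the basal-bolus figures as total daily insulin, so that glargine = 0.5 × total:

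- 0.5 × 0.4 = 0.20 units/kg/day
- 0.5 × 0.5 = 0.25 units/kg/day

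Both match the basal-only glargine doses exactly. Now treat them as glargine and give an equal amount of lispro to satisfy the split:

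- 0.4 + 0.4 = 0.8 units/kg/day in total
- 0.5 + 0.5 = 1.0 units/kg/day in total

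That is double the total under the first reading, and glargine no longer matches the other table.

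**Step 2: size of the discrepancy.** Ratio of glargine by the heading to glargine by the split rule = 0.4 / 0.2 = 0.5 / 0.25 = 2. Weight cancels.

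| Case | By heading (units) | Indicated (units) |
|---|---|---|
| 100 kg, GFR ≥50, glucose 140-200 | 0.4 × 100 = 40 | 20 |
| 100 kg, GFR ≥50, glucose 201-400 | 0.5 × 100 = 50 | 25 |
| 70 kg, GFR ≥50, glucose 140-200 | 28 | 14 |
| 70 kg, GFR ≥50, glucose 201-400 | 35 | 17.5 |
| 120 kg, GFR ≥50, glucose 140-200 | 48 | 24 |
| 120 kg, GFR ≥50, glucose 201-400 | 60 | 30 |
| 100 kg, GFR <50, glucose 140-200 | 20 | 10 |
| 100 kg, GFR <50, glucose 201-400 | 25 | 12.5 |

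The renal rule halves both readings, so the ratio stays at 2.

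**Step 3: how far would titration correct a doubled start?** Doses are expressed as multiples of the indicated starting dose:

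- one 10% cut (glucose 70-99): 2 × 0.9 = 1.80
- one 20% cut (glucose below 70): 2 × 0.8 = 1.60
- one 30-40% cut (glucose below 40): 2 × 0.7 = 1.40 to 2 × 0.6 = 1.20
- a 10% cut and a 20% cut: 2 × 0.9 × 0.8 = 1.44
- a 10% cut on each of Days 2-5: 2 × 0.9⁴ = 1.31

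These are conditional sequences, not a forecast. At 100-140 mg/dL without hypoglycemia the rule leaves the dose alone, and above 140 it raises it.

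**The case against.** The best reply is that the table corrects itself. The split rule comes straight after the dose rows, lispro cannot be ordered without it, and applying it to the listed figures gives the right glargine dose. That would indeed lead most readers to the correct order. It does not settle the matter, because glargine 0.4 with an equal 0.4 of lispro also satisfies both lines as written, so a doubled dose does not strictly require the split rule to be ignored.

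Other points stand as limits:

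- The rule that assigns patients to this regimen is not visible in the available text, so the number exposed cannot be stated.
- Full glargine during fasting at a GFR of 50 or above applies to the correct dose too. It is not caused by the heading; it only means that a doubled dose would not be reduced for poor intake.
- The titration multiples compare a titrated dose with an untitrated starting dose. If the same percentage cuts applied under both readings, the ratio would stay at 2.
- Safeguards exist: glucose is checked four times daily, glargine is reduced before hypoglycemia occurs, the hospital hypoglycemia protocol applies below 70 mg/dL, and lispro is withheld from patients who are not eating. Section 5.1 also provides for reduced basal insulin in patients who need large doses, although that concerns continuing treatment more than a weight-based start.

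**Conclusion.** The concern holds: the heading is wrong for the basal-bolus rows as written. The discrepancy is a factor of exactly 2 in starting glargine at any weight or GFR. The unit figures depend on the assumed weights.

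That 0.2 and 0.25 units/kg/day are the intended glargine doses is an inference, since no row is labelled as a total. It is well supported by the split rule, the absence of a separate lispro dose and the exact match with the basal-only table. Whether any site would actually double the dose is unknown.

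The heading is the same in both arms, and the primary and secondary endpoints do not use insulin dose, so this is a patient-safety wording error and not a threat to the main inference. It should be corrected.

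**What to change.** Retitle the basal-bolus heading *Total daily insulin (glargine + lispro): starting dose*. Once the sponsor confirms the intended doses, state them directly: glargine 0.2 or 0.25 units/kg/day once daily by glucose band, and the same daily amount of lispro in three equal post-meal doses. Leave the basal-only heading as it is. Send sites a short clarification.

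The cost is one heading and its dose lines in one appendix table, plus a site notice. Nothing changes in the design, sample size or analysis.
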